3.2.4.2 Derivations

Not applicable.

3.2.4.3 Handling of Dropouts and Missing Data

The populations of interest do not include participants withdrawing before Week 13 and participants with one of the two measurements missing and so will not be included in the analysis.

3.2.4.4 Primary Analysis of Secondary Endpoint 3

For secondary objective 3, a scatter plot will be used to display changes from baseline at Week 13 in each imaging endpoint (including: all FRI endpoints in Table 2) against changes from baseline at Week 13 in each conventional lung function measure (including: pre-BD FEV₁ and pre-BD FVC). Both Spearman's rank and Pearson correlation coefficients will be used to describe the strength of the association between changes from baseline at Week 13 in each imaging endpoint and both of the conventional lung function measures. Estimated correlation coefficients will be reported with corresponding 95% CIs and p-values, testing the null hypothesis of no correlation.

Changes from baseline in conventional lung function measures at Week 13 may be related to baseline values. Therefore, correlation coefficients between each imaging parameter and conventional lung function measure will be reported for the overall populations and for two subgroups, based on dichotomizing at the median baseline value.

To estimate the average change from baseline (Week 13 versus Week 0) in each imaging endpoint, a linear regression model for the change from baseline in each imaging endpoint will be fitted, with adjustment for the baseline (Week 0) measurement of the imaging endpoint. The model will be fitted with and without the inclusion of the change from baseline in pre-BD FEV₁ and pre-BD FVC as individual covariates. Models including and excluding conventional lung function measures as covariates are defined below and are referred to as adjusted and unadjusted models, respectively.

The adjusted linear regression model will be as follows:

$$y_i = \beta_0 + \beta_1 x_{1i} + \beta_2 x_{2i}$$

Where:

• y_i is the change from baseline at Week 13 in the imaging endpoint
- β_0 quantifies the average change from baseline at Week 13 in the imaging endpoint after accounting for the baseline value
- x_{li} is the baseline value at Week 0 of the imaging endpoint
- β₁ quantifies the association between Y and x₁
- x_{2i} is the change from baseline at Week 13 in the conventional lung function measure
- β₂ quantifies the association between Y and x₂, after accounting for baseline measurements

The unadjusted linear regression model will be as follows:

$$y_i = \beta_0 + \beta_1 x_{1i}$$

Where:

- y_i is the change from baseline at Week 13 in the imaging endpoint
- β₀ quantifies the average change from baseline at Week 13 in the imaging endpoint after accounting for the baseline value
- x_{li} is the baseline value at Week 0 of the imaging endpoint
- β₁ quantifies the association between Y and x₁, after accounting for baseline measurements

Two adjusted and unadjusted models will be fitted for each imaging endpoint, where the conventional lung function measure is pre-BD FEV_1 for model (i) and pre-BD FVC for model (ii).

Estimated regression coefficients for the intercept, β_0 , from the unadjusted and adjusted models will be reported with 95% CIs and p-values, and compared to indicate whether the average change from baseline in the imaging parameter is explained by changes from baseline in pre-BD FEV₁ and pre-BD FVC. Estimated regression coefficients, β_2 , for changes in pre-BD FEV₁ and pre-BD FVC will be reported with 95% CIs and p-values, to quantify the average change in each imaging endpoint for every one percent increase in pre-BD FEV₁ and pre-BD FVC.

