Statistical methods used for the primary objective and secondary objective 1 will be univariate paired *t*-tests and mixed effects modelling. Scatter plots and correlation calculations will be used to assess the baseline association between all FRI parameters of interest and conventional lung function measures, FEV₁ and FVC, for the secondary objective 2. For secondary objective 2, linear regression models will also be fitted to quantify the baseline relationship between each FRI endpoint of interest and the conventional lung function measures. For secondary objective 3, scatter plots and correlation calculations will be used to assess the association between change from baseline in each FRI parameter and change from baseline in the conventional measures. For secondary objective 3, a linear model for FRI endpoints will also be estimated, both adjusted for FEV₁ and FVC and unadjusted for these measurements. These models will include an indicator variable for week 13 to quantify the change from baseline in FRI endpoints. Additional details and methods for other outcomes are provided in Section 9.4.2.

The sample size estimate required to detect a change from baseline in the primary endpoint (untrimmed total mucus volume at TLC) is 29 participants. This estimate is based on results from another study of a biologic treatment and FRI parameters, with the calculation details and corresponding assumptions enumerated in Section 9.2.

Safety analyses will be performed using the safety analysis set. Safety data will be presented using descriptive statistics unless otherwise specified.

The populations to be analyzed consist of:

- Participants who completed the study per protocol definition and had no exacerbation during the study period (primary analysis population)
- All participants who completed the study per protocol definition
- Participants who completed baseline measurements at Visit 1 and had at least one dose of IP, irrespectively of whether they discontinued for reasons as described in Section 7.1 (the baseline endpoints analysis set).
- Subgroup analyses
 - Mucus plugging status: Participants with or without mucus plugs identified using CT scans (Section 8.1.1.2) taken at Visit 1 (week 0)
 - OCS dependency status: OCS-dependent and Non-OCS-dependent participants as defined by the inclusion criteria #4 (Section 5.1)

[figure not shown]
No interim analyses have been planned for this study.

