A linear regression model for imaging endpoints will be fitted, consisting of a binary explanatory variable (corresponding to week 13). The regression coefficient for time will estimate the change from baseline (week 13 vs week 0) in the imaging endpoint. The model will be fitted with and without the inclusion of the change from baseline in pre-BD FEV₁ and pre-BD FVC as individual covariates. Estimated regression coefficients for time from the unadjusted and adjusted models will be compared, to indicate whether the change from baseline in the imaging parameter is explained by changes in pre-BD FEV₁ and pre-BD FVC. Estimated regression coefficients for changes in pre-BD FVC will be reported, to quantify the average change in each imaging endpoint for every one percent increase in pre-BD FEV₁ and pre-BD FVC.

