Section 3.6.2: Adverse events	09/11/2023	AEs collection dates specified	Yes (v 4.0)	Clarification required
Section 5: References	09/11/2023	New references added	Yes (v 4.0)	Clarification required
Section 6: Appendix	09/11/2023	New appendix added	Yes (v 4.0)	Clarification required
Section 2.3: General considerations	22/01/2024	Table 2 edited: proposed rank removed; abbreviations added, endpoints with proposed rank >7 removed except con	Yes (v 5.0)	Updated as in CSP
Section 3.2: Endpoint analysis	22/01/2024	Table 3 edited, clarification of some endpoints	Yes (v 5.0)	Clarification required
Section 3.2.1: Primary Endpoint – Change from Baseline (Week 0) to week 13 in airway dynamics, using untrimmed total mucus volume at TLC	22/01/2024	Changes to endpoints	Yes (v 5.0)	Endpoint changes to CSP v 5.0
Section 3.2.1.5: Secondary analysis of primary endpoint	22/01/2024	Mixed model equation added	Yes (v 5.0)	Clarification required

STATISTICAL ANALYSIS PLAN D3250R00107 – ed. 2.0

CATEGORY Change refers to:	Date	Description of change	In line with CSP?	Rationale
Section 3.1.6.1 Disease characteristics. Definitions and derivations	12/02/2024	Imputation rules added	Yes (v 5.0)	Clarification required
Section 3.2.4 Secondary Endpoint 3	13/02/2024	Analysis set removed, except Primary analysis set	Yes (v 5.0)	Population removed to streamline analysis
Section 3.2.5 Tertiary Endpoint 1	13/02/2024	Analysis set removed, except Baseline endpoints analysis set	Yes (v 5.0)	Population removed to streamline analysis
Section 3.2.6 Tertiary Endpoint 2	13/02/2024	Analysis set removed, except Primary analysis set	Yes (v 5.0)	Population removed to streamline analysis
Section 3.2.3 Secondary Endpoint 2	16/02/2024	Analysis set removed, except Baseline endpoints analysis set	Yes (v 5.0)	Population removed to streamline analysis

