3 STATISTICAL ANALYSIS

This section provides information on definitions, derivation and analysis/data presentation per domain.

All continuous variables, including FRI parameters (Table 2), pre-BD FEV₁, pre-BD FVC, CCI , will be summarized using means, standard deviation (SD) and 95% ranges, or medians and inter-quartile ranges, depending on the distributions of the data. Mean changes from baseline in continuous variables will be reported, including asymptotic 95% confidence interval (CI). Categorical data (eg, CCI

) will be summarized as the number and

percentage among participants with non-missing data. Descriptive statistics will be calculated for the data stratified by gender. Unless otherwise stated, all hypothesis tests are two-sided and all hypothesis tests will be performed at a 5% significance level. Analyses will be carried out for overall participants and subgroups as specified in Section 3.2.1.8. FRI parameters may be log-transformed prior to analysis to reduce skewness.

All report outputs will be produced using SAS® version 9.4 or a later version in a secure and validated environment.

For continuous data, mean, and upper and lower quartiles will be rounded to one additional decimal place compared to the original data. The SD will be rounded to one additional decimal place compared to the original data. Median, minimum and maximum will be displayed with the same accuracy as the original data. For categorical data, percentages will be rounded to one decimal place, percentages will not be shown for 0, decimal places will not be shown for 100%.

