2.7 Linear Regression Model

In SAP sections 3.2.4 and 3.2.6, it states that more than just the intercept should be displayed in the final outputs however it is the intercept which is of interest and should be reported.

Linear regression models that have a population n < 10 will not be shown in the final outputs.

Throughout the linear regression sections of the SAP there is certain wording that requires more clarity. So, the following sections outline the number of model that should be used for each endpoint.

2.7.1 Secondary Endpoint 3 - Relationship Between Changes from Baseline in Airway Dynamics and Lung Functions Measurements at Week 13

The use of the word unadjusted in the SAP causes confusion over the number of models. Instead, the number of models is outlined explicitly. Three linear models will be fitted for each imaging parameter, where the endpoint will be change from baseline to week 13 in the imaging parameter:

- Model 1: Adjustment for baseline measurement of imaging parameter only
- Model 2: Adjustment for baseline measurement of imaging parameter and for change from baseline to week 13 in pre-BD FEV1
- Model 3: Adjustment for baseline measurement of imaging parameter and for change from baseline to week 13 in pre-BD FVC

CONFIDENTIAL

Developed from TP-BPM-WW-032; related to SOP-BPM-WW-001 D3250R00107

Statistical Analysis Plan Addendum

Table 4outlines the models that are expected for the analysis of tertiary endpoint 1.

Should there be no data for the assigned reference category then the most abundant category will be assigned as the reference.

Table 5 outlines all the of models expected for tertiary endpoint 2

Project Document Version No.: 3.0; Document Effective Date: 03 Sep 24 TP-GDO-WW-169-01 Effective Date: 22 Dec 21 Related to: SOP-GDO-WW-019 CONFIDENTIAL

Developed from TP-BPM-WW-032; related to SOP-BPM-WW-001 D3250R00107

Statistical Analysis Plan Addendum

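### Whether lung-function change explains imaging change is to be read from two intercepts side by side; their difference is never estimated, and the addendum drops the coefficient that would show it

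*SAP*

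**What the plan says.** SAP 3.2.4.4 sets out two linear models for the change in an imaging endpoint. The unadjusted model has the endpoint's baseline as its only covariate. The adjusted model adds x2, which "is the change from baseline at Week 13 in the conventional lung function measure", with no centring. In both models the SAP says that β0 "quantifies the average change from baseline at Week 13 in the imaging endpoint after accounting for the baseline value". Each intercept gets its own 95% CI and p-value, and the two are "compared to indicate whether the average change from baseline in the imaging parameter is explained by changes from baseline" in FEV1 and FVC. The same paragraph also plans to report β2, the coefficient of lung-function change, with a CI and p-value.

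Addendum 2.7 notes that the SAP would display more than the intercept, but that "it is the intercept which is of interest and should be reported". Addendum 2.7.1 then lists three models: baseline only (Model 1), baseline plus FEV1 change (Model 2), and baseline plus FVC change (Model 3).

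Protocol 9.4.2.2 describes another form. It regresses the imaging endpoint on a week-13 indicator, with and without the change in FEV1 and FVC: "Estimated regression coefficients for time from the unadjusted and adjusted models will be compared".

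None of these places gives an estimate, interval, test or threshold for the difference between the two coefficients. Sensitivity and supplementary analyses for this endpoint are marked not applicable.

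**The concern.** Objective 3 is where the trial connects imaging change to lung function. The quantity that answers the question is how far the intercept moves when lung-function change is added, and the plan never estimates that movement.

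The two intercepts also estimate different things. With x2 uncentred, the adjusted intercept is the predicted imaging change for a participant whose FEV1 (or FVC) did not change. That is not the average change the SAP says it is. If lung function improves on average, this prediction lies away from the centre of the data and is usually less precise, even when lung function has nothing to do with imaging. A reader who sees a significant intercept become non-significant could then conclude that lung function accounts for the change when nothing has been explained. The planned β2 would warn of this, but the addendum's intercept-only wording removes it.

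**Working it through.** **Inputs from the documents.** Tests: "all hypothesis tests are two-sided and all hypothesis tests will be performed at a 5% significance level" (SAP section 3). Planned number to detect a change in the primary endpoint: "untrimmed total mucus volume at TLC) is 29 participants" (Protocol synopsis). Population for secondary endpoint 3: "Analysis set removed, except Primary analysis set" (SAP amendment history).

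**Inputs assumed.** The effect size, SD and power behind 29 are redacted, so 29 cannot be reproduced. It can only be inverted. For a two-sided 5% paired t-test with n=29, the standardised change is 0.54 for 80% power and 0.62 for 90%. The ratio m = mean/SD of the lung-function change is not in the documents and is ranged. Data are taken as normal.

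**The quantity of interest.** With the imaging baseline centred at its sample mean, Model 1 gives β0 = mean imaging change. Model 2 gives β0 = mean imaging change − β2 × mean lung-function change. So

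β0(Model 1) − β0(Model 2) = β2 × mean lung-function change.

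This identity is exact and held in the simulations. If the lung-function change were centred too, both intercepts would equal the mean imaging change and the comparison could show nothing.

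**Precision.** With rho the correlation of imaging change and lung-function change given baseline, in large samples

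(SE adjusted / SE unadjusted)² ≈ (1 − rho²)(1 + m²).

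**Nothing explained (β2 = 0, so rho = 0).** 20,000 simulated trials per setting, n=29, imaging change 0.54 SD, baseline centred:

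| m | √(1+m²) | Median SE ratio | Unadjusted significant | Adjusted significant | Significant, then not (all trials) | As share of those first significant |
|---|---|---|---|---|---|---|
| 0 | 1.00 | 1.02 | 80.9% | 79.2% | 3% | 4% |
| 0.25 | 1.03 | 1.04 | 80.3% | 75.9% | 6% | 8% |
| 0.5 | 1.12 | 1.13 | 79.7% | 68.5% | 13% | 17% |
| 0.75 | 1.25 | 1.27 | 80.1% | 58.3% | 24% | 30% |
| 1.0 | 1.41 | 1.45 | 80.3% | 49.0% | 33% | 42% |
| 1.5 | 1.80 | 1.87 | 80.3% | 33.5% | 49% | 60% |

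The mean difference between intercepts stays within 0.004 SD of zero, so the switches come from lost precision and chance, not from a systematic shift. At 0.62 SD the switch rates are 2%, 5%, 11%, 21%, 31% and 49%.

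**Baseline left uncentred, as the SAP formula has it.** With the baseline mean assumed at 1 SD, the switch rate is about 8 to 9% at m=0.5 and 19 to 20% at m=1.0 (spread between simulation runs).

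**Would β2 expose the misreading?** At m = 0.5, 0.75 and 1.0, β2 is itself significant in only 1.0, 1.7 and 1.9 percentage points out of the 13, 24 and 33. Reporting β2 would flag nearly all of these cases.

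**Does an interval for the difference behave better?** Participant-level bootstrap percentile 95% CI (999 resamples, 1,500 trials, n=29): with β2=0 it excludes zero in 5.3% of trials at m=0.5 and 7.3% at m=1.0, against 13.4% and 33.4% for the switch in significance. With rho=−0.5 it excludes zero in 60% and 79%.

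**Protocol form.** If a participant's FEV1 change has the same value in the week-0 and week-13 rows, it is uncorrelated with the week-13 indicator, and adding it cannot move the time coefficient. In a constructed data set where FEV1 change drives imaging change, the coefficient was −0.5951 both without and with the covariate.

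**The case against.** **The plan does not make loss of significance its criterion.** This is correct. A reader might infer that the SAP decides explanation by p-value, but the documents leave the comparison undefined. Subtracting the two printed intercepts would give a point difference centred on zero when nothing is explained. The misreading is a risk the plan leaves open, not a rule it states.

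**Adjustment does not always cost precision.** Also correct. With β2=0 the SE still falls in about 21%, 13% and 3% of trials at m = 0, 0.25 and 0.5. Where lung function is related to imaging, precision can improve: at rho=−0.5 the median SE ratio is 0.89, 0.92 and 0.99 at m = 0, 0.25 and 0.5, and at rho=−0.7 it is 0.82 at m=0.5.

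**The total share of non-significant adjusted intercepts overstates the harm.** From the table this is about 32%, 42% and 51% at m = 0.5, 0.75 and 1.0, but about 20% were non-significant before adjustment. The switch rate is the relevant figure.

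**Safeguards remain.** SAP 3.2.4.4 keeps the correlations between changes, with CIs and p-values. They help, but they do not say how much of the mean imaging change goes with lung function. Addendum 2.8.2 and 2.11.2 give rounding rules for regression coefficients, but do not say that β2 is among those reported.

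**The protocol form need not fail.** A reader might infer that it guarantees a finding of no explanation. That holds only if the change is coded as a participant constant. Protocol 9.4.2.2 supports that reading, but the synopsis speaks of adjusting for FEV1 and FVC themselves. In one constructed data set the time coefficient was −0.593 unadjusted, −0.593 with the constant, −0.532 with visit-level FEV1, and +0.066 with the change coded zero at week 0. The SAP's change-score model in any case supersedes this form.

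**The objective is secondary and descriptive, with no success rule.** True. This limits the weight of the point but does not make the comparison interpretable.

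**Conclusion.** The point holds in a limited form. The plan names a comparison meant to answer objective 3 but does not estimate the quantity compared. It describes the adjusted intercept as an average change, which it is not, and the addendum removes the coefficient that would best protect the reader.

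If the intercepts are compared through their p-values, a false reading of explanation would arise in about 6% to 33% of trials as m runs from 0.25 to 1.0. This assumes n=29, β2=0, a centred imaging baseline, normal data and a 0.54 SD imaging change. The rate is lower with the baseline uncentred and close to negligible if lung function does not change on average. The true m is unknown from the documents, so no single rate can be claimed. The primary endpoint analysis is unaffected.

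**What to change.** In SAP 3.2.4.4 and Addendum 2.7 and 2.7.1:

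- Centre the imaging baseline, but not the lung-function change, and describe the adjusted intercept as the predicted change at zero lung-function change.
- Report β2 with its 95% CI and p-value, as the SAP planned.
- Report Model 1 minus Model 2, and Model 1 minus Model 3, each with a participant-level bootstrap 95% CI, repeating the centring and both fits in every resample.
- Base any statement that lung function explains the imaging change on that interval, not on the adjusted intercept's p-value.
- Fit the models being compared to the same participants. Addendum 1.1 lets participants without spirometry into the analysis set, and otherwise the difference would also reflect a change of sample.

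Align Protocol 9.4.2.2 and the synopsis with the SAP change-score model, dropping the week-13-indicator form.

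The cost is a wording change and a short bootstrap on models already planned, with no new data. At about 29 participants the interval will often be wide, so fewer statements about explanation will be possible. The percentile interval is also slightly liberal (7.3% at m=1.0 against a nominal 5%).

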3.2.4.5 Sensitivity Analyses of the Secondary Endpoint

Not applicable.

3.2.4.6 Supplementary Analyses of the Secondary Endpoint

Not applicable.

3.2.4.7 Subgroup Analyses

Subgroup analysis is described in Section 3.2.1.8.

3.2.5	CCI	
	CCI)

3.2.5.1 Definition

Table 8Definition of CCEndpoint 1

Population:	
Endpoint:	
Treatment	Benralizumah 30 mg 3 doses, once every 4 weeks (at baseline [V1]. Week 4 [V2]
Treatment.	and Week 8 [V3])
Intercurrent events:	Participant withdrawal, IPD, use of prohibited medicines/substances, asthma exacerbation
Population-level summary:	Spearman's rank correlation coefficientsRegression coefficients with 95% CI

3.2.5.2 Derivations

STATISTICAL ANALYSIS PLAN D3250R00107 – ed. 2.0

CCI
CCI

3.2.5.3 Handling of Dropouts and Missing Data

Participants with missing baseline (Week 0) measurements do not form part of the analysis populations and will not be included in the analysis.

3.2.5.4 Primary Analysis of CC Endpoint 1

Correlation (Spearman's rank) coefficients, with 95% CIs, will be reported to describe the strength of the association between each imaging endpoint (including: all FRI parameters) and CCI at baseline (Week 0).

CCI		
	·	
CCI		
CCI		

Linear regression models will be used to model the relationship between each imaging endpoint and CCI will estimate the average increase in imaging endpoints at Week 0 for CCI of 2-4 and 5-10 versus 0-1 at Week 0. Estimated regression coefficients will be reported together with 95% CIs.

Similarly, linear regression models will be used to estimate the average increase in each imaging endpoint at Week 0, with the 95% CI, for Yes versus No responses at Week 0 to 2, 4, and 8, separately.

We will also estimate the average increase in imaging parameters at baseline for well controlled and partly controlled vs. not well controlled **CC** at Week 0), based on linear regression modelling.

